#### 4.16. ARI MISSING DATA

During the day of vaccination, the end of season visits, the ARI Day 3-5 and ARI Day 29 visit the site will collect the reason for missingness in case there are missing ePro assessments at the sites eDevice. These reasons will be tabulated at baseline and end of season for all participants per assessment and per group. For any ARI episode and for any RT-PCR confirmed RSV ARI the reason of missingness of the different assessments will similarly be tabulated.

Moreover, based on the RiiQ assessments descriptive statistics of the number of days with missing assessments during the first 7 days of an ARI episode, the first 14 days of an ARI episode and during the full ARI episode will be summarized per group. Finally, the percentage of compliance based on the RiiQ assessments will be calculated as follows:

- Compliance over the whole episode is defined as:  $\text{Nr of days with RiiQ assessments} / \text{duration of episode} \times 100$
- Compliance during the first seven days is defined as:  $\text{Nr of days with RiiQ assessments between day 1 and day 7} / \text{min (duration episode, 7 days)} \times 100$
- Compliance during the first 14 days is defined as:  $\text{Nr of days with RiiQ assessments between day 1 and day 14} / \text{min (duration episode, 14 days)} \times 100$

For example: For a subject with an ARI episode duration of 21 days with missing RiiQ assessment on day 4, 8 and 19, the compliance over the whole episode is  $18/21 \times 100$ , the compliance during the 1st 7 days is  $6/7 \times 100$ , the compliance over the 1st 14 days is  $12/14 \times 100$ .

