#### **4.4.2.1.3. ARI Episode Duration**

The duration of an ARI episode is defined as: *Last day of symptoms above baseline - start date of ARI + 1*. The ARI Day 1 and ARI Day 3-5 visits are always taken into account for the duration if there is a new onset or worsening of a symptom. The ARI Day 29 is taken into account for the duration only if the RiiQ assessments reported by the participants on his/her home device go up to or exceed the ARI Day 29 visit date (actual date). In this case, ARI Day 29 site assessments occurring after this last RiiQ assessment reported by the participants on his/her home device (actual day) are not taken into account for the duration. End of Season as well as Day 365 and Day 730 visits are excluded when determining ARI end dates. Only URTI and LRTI symptoms from clinical assessment and patient reported outcome will be used in calculating the duration of an ARI episode (Table 8).

Moreover, for ARIs with no new onset or worsening of symptoms, duration will not be calculated.

For calculating the ARI duration, the following rules may be used:

- For all ARIs the start dates are reported in the CRF (=CE.CESTDTC where CETERM=ACUTE RESPIRATORY INFECTION and CE.CECAT= ‘’).

- Then a temporary end date for each ARI is created:
  - In case a participant has multiple ARIs, the temporary end date is set as a day before the start of the next ARI.
  - In case a participant has only one ARI, the temporary end date is set as the day of database cut off (15 May 2020).
- Search between the ARI start date and the temporary end date, for the last date the participant had a new onset or worsening of URTI or LRTI symptoms (Table 8), at the RiiQ assessments completed on his /her device and set it as ‘*enddate1*’.
- If the RiiQ assessments, between the ARI start date and the temporary end date, reported by the participants on his/her home device do not reach the actual ARI Day 29 visit date. Search between the ‘ARI Day 1’ and ‘ARI Day 3-5’ visits (both scheduled and unscheduled), for the last date the participant had a new onset or worsening of URTI or LRTI symptoms (Table 8), at the assessments collected during these visits and set it as ‘*enddate2*’.

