#### **5.15. ARI MISSING DATA**

The same analysis as in the first RSV season will be conducted, for the second and third RSV season for ARI missing data. See Section 4.16.

---

a For participants without a Day 730 visit, the second RSV season will be cut off at the relative Day 730 (given that they did not discontinue before) to calculate the number of weeks in step 1. Additionally, ARIs starting in the second RSV season lasting longer than this relative Day 730 will also be cut off at the relative Day 730 in step 2. Finally, when calculating the number of surveillance questions answered, the ones after this relative Day 730 visit will not be counted.

---

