**Source:**

Graf C. The Lawton instrumental activities of daily living scale. Am J Nurs. 2008;108(4):52-62.

**Attachment 8: Examples of ARI Duration Calculations****Example 1:** If a participant had:

- ARI start date: 10/11
- RiiQ assessments on his device: 10/11 - 16/11
- ARI Day 3-5 visit: 14/11
- ARI Day 29 visit: 8/12
- New onset or worsening of LRTI or URTI:
  - RiiQ at subject's device: 10/11-11/11
  - Planned visits: 14/11 and 8/12

Then the ARI episode end date is 14/11 (= max [enddate1, enddate2] = max [11/11, 14/11]) and the duration is 5 days. In case the same participant did not had a new onset or worsening during the ARI Day 3-5 visit then the end date would be 11/11 and the duration 2 days.

	ARI start (CE domain)				ARI Day 3-5 Visit	Duration
	10/11	11/11	12/11	13/11	14/11	
1	New onset or worsening	New onset or worsening			New onset or worsening	5 days
2	New onset or worsening	New onset or worsening				2 days

Some additional examples below, given the RiiQ assessments reported by the participants on his/her home device do not reach the actual ARI Day 29 visit date:

	ARI start (CE domain)				ARI Day 3-5 Visit	ARI Day 3-5 Unsch. Visit	Duration
	10/11	11/11	12/11	13/11	14/11	15/11	16/11
1	New onset or worsening	New onset or worsening			New onset or worsening	New onset or worsening	7 days
2	New onset or worsening	New onset or worsening			New onset or worsening		5 days
3	New onset or worsening					New onset or worsening	7 days
4	New onset or worsening						1 day

	ARI start (CE domain)				ARI Day 1 Unsch. Visit	ARI Day 3-5 Visit	Duration
	10/11	11/11	12/11	13/11	14/11	15/11	16/11
1	New onset or worsening	New onset or worsening			New onset or worsening	New onset or worsening	7 days
2	New onset or worsening	New onset or worsening			New onset or worsening		5 days
3	New onset or worsening	New onset or worsening				New onset or worsening	7 days

**Example 2:** If a participant had:

- ARI start date: 1/11
- ARI Day 3-5 visit: 4/11
- ARI Day 29 visit: 29/11
- New onset or worsening of LRTI or URTI :
  - RiiQ at subject's device: 1/11-10/11
  - Planned visits: 4/11 and 29/11

If the participant completed the RiiQ assessments from the 1/11 to the 27/11 then the end date would be 10/11 and the duration 10 days. Whereas, if the participant completed the RiiQ assessments from the 1/11 to the 29/11 or to the 30/11 then the end date would be the 29/11 and the duration would be 29 days.

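### RiiQ compliance in SAP section 4.16 does not confine the numerator to episode days, so read literally it can exceed 100%, and it can read 100% for some participants who stop the diary while still ill

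*SAP*

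**What the plan says.** Section 4.16 defines three percentages.

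- First 7 days: "Nr of days with RiiQ assessments between day 1 and day 7", divided by "min (duration episode, 7 days").
- First 14 days: "Nr of days with RiiQ assessments between day 1 and day 14", divided by "min (duration episode, 14 days").
- Whole episode: the number of days with a RiiQ divided by the episode duration, with no window stated for the numerator.

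Section 4.4.2.1.3 defines the duration as "Last day of symptoms above baseline - start date of ARI + 1". It always uses the ARI Day 1 and Day 3-5 visits if they show a new or worsened symptom. The Day 29 visit is treated differently: "The ARI Day 29 is taken into account for the duration only if the RiiQ assessments reported by the participants" on the home device reach that visit.

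Attachment 8 illustrates duration with participants whose diary runs past the last symptomatic day. Example 1 has "RiiQ assessments on his device: 10/11 - 16/11" and a duration of 5 days.

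Section 5.15 carries the measure forward: "The same analysis as in the first RSV season will be conducted, for the second and third RSV season for ARI missing data".

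**The concern.** Numerator and denominator cover different sets of days. The denominator stops at the end of the episode. The numerator runs to day 7, to day 14 or without limit. A diary completed after recovery therefore adds to the count of compliant days but not to the days expected, and a compliance percentage above 100% has no meaning.

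The denominator also depends on the participant's own reporting. If the diary stops while symptoms persist, and no later qualifying visit records a symptom, the recorded episode ends on the last diary day. The percentage then cannot show that the diary stopped early.

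What is at stake is the description of RiiQ completeness. The daily diary is one of the assessments from which the case definitions are counted (section 4.4.2.1.1), so a reader will use this table to judge how well symptoms were captured.

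**Working it through.** **Rule applied.** For k = 7 or 14, compliance = RiiQ days in days 1 to k, divided by min(duration, k). For the whole episode, compliance = all RiiQ days divided by duration. I count days with a home-device RiiQ. Section 4.16 does not say whether a RiiQ on the site device also counts as a day. In the 7- and 14-day windows of Examples 1 and 2 this makes no difference, because the Day 3-5 visit falls on a diary day.

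**The SAP's own figure.** Section 4.16 takes a 21-day episode with days 4, 8 and 19 missing. Whole episode: (21 − 3)/21 = 18/21 = 85.7%. First 7 days: 6/7 = 85.7%. First 14 days: 12/14 = 85.7%. All three agree with the SAP. The duration exceeds both windows, so this example cannot reveal the mismatch.

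**Attachment 8, Example 1.** Diary 10/11 to 16/11 = days 1 to 7. The last counted symptomatic day is 14/11, so duration = 14 − 10 + 1 = 5.
- First 7 days: 7/min(5, 7) = 7/5 = 140%.
- Variant with no symptom at the Day 3-5 visit (duration 2): 7/min(2, 7) = 7/2 = 350%.

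**Attachment 8, Example 2.** Diary 1/11 to 27/11 = 27 days; duration 10.
- First 7 days: 7/min(10, 7) = 7/7 = 100%.
- First 14 days: 14/min(10, 14) = 14/10 = 140%.
- Whole episode: 27/10 = 270%.

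**Attachment 8, the second case labelled Example 3.** Diary on days 5 and 6 only; duration 5. First 7 days: 2/5 = 40%, although only one of those diary days lies inside the episode (1/5 = 20%). The measure can be inflated without passing 100%.

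**With the numerator limited to the denominator window.** Example 1: 5/5 = 100%. Its variant: 2/2 = 100%. Example 2: 10/10 = 100% for 14 days and for the whole episode. The 21-day example is unchanged at 85.7%.

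**Stopping early (assumed case).** The participant reports symptoms on days 1 to s, then makes no further diary entry, and is still ill. No symptomatic Day 1 or Day 3-5 assessment falls after day s. The Day 29 visit is ignored because the diary did not reach it. Duration = s, so all three measures equal s/s = 100% for s = 2 to 6. Limiting the numerator does not change this.

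**Where that stops being true.** A symptomatic Day 3-5 visit after the last diary day lengthens the denominator. With the visit on day 4, a diary to day 2 gives 2/4 = 50%, and a diary to day 3 gives 3/4 = 75%.

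**The case against.** The strongest reply is that section 4.16 plainly intends episode days. It first counts missing days within the episode, it labels one formula as covering the whole episode, and its example subtracts missing days from the duration. Taking the smaller of duration and 7 or 14 also cuts the window at the episode's end. Attachment 8 was written to show duration, not compliance. Read that way, no value exceeds 100%. This may well be the intent. But the limit is not written down, the 7- and 14-day formulas name their own numerator windows, and a programmer who follows them gets 140% from the SAP's own cases.

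Several stronger readings are tempting, and the SAP does not support them.

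- A reader might infer that everyone who stops reporting early looks fully compliant. The Day 1 and Day 3-5 rule prevents that for many of the earliest stoppers, as the 50% and 75% results show.
- One could assume a 21-day illness and set 5/21 = 24% against 5/5 = 100%. That length is invented, and the trial would not observe the true end of such an illness.
- Missed cases do not simply follow. The Day 3-5 visit supplies a site-device RiiQ and a staff assessment, and either can meet a case definition alone.
- It might be called the main completeness measure, with values over 100% cancelling gaps elsewhere. The SAP gives it no such rank. It also summarises missing-day counts and reasons for missing site assessments, and it names no summary statistic for these percentages.

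A fixed 7- or 14-day denominator is not a clean replacement either. A participant with a 2-day illness who stopped the diary on recovery would score 2/7 = 29% or 2/14 = 14%.

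**Conclusion.** The point holds in two limited parts. First, as written, the compliance formulas exceed 100% whenever enough diaries are completed after symptoms settle: 140% and 350% in Example 1 and its variant, and 140% and 270% in Example 2. This rests on a literal reading of the numerator, which no text in section 4.16 restricts. Second, under either reading, a participant who stops the diary while still ill scores 100%, provided no later symptomatic Day 1 or Day 3-5 assessment exists. How often that happens cannot be judged from the SAP.

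A reader might infer that efficacy results are affected. They are not: nothing in the SAP uses this percentage to define an analysis set, enter the efficacy model or drive imputation, which concerns RT-PCR results. The consequence is a descriptive table in seasons 1 to 3 that can show impossible or uninformative values.

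**What to change.** In section 4.16, restrict each numerator to its denominator window: RiiQ days from day 1 to min(duration, 7), from day 1 to min(duration, 14), and from day 1 to duration. Section 5.15 inherits the change.

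Add a sentence stating that duration is set by the last recorded symptomatic day and omits the Day 29 visit when the home diary ends before it. The percentage therefore cannot show diary dropout that no later symptomatic Day 1 or Day 3-5 assessment follows.

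Optionally, show the number of RiiQ days completed in days 1-7 and 1-14 from the ARI start date in the CE domain. Label it as a supplementary description that will read low for participants who recover quickly.

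The cost is a short wording change and a rerun of one descriptive table. Compliance figures will stay the same or fall.

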#### 4.17. Post-hoc Analyses

Post-hoc some additional analyses were added for season 1.

- Complications aligned with the phase 3 efficacy study (see Section 5.4.1)
- Clinical Relevant Diseases definition aligned with the phase 3 efficacy study (see Section 5.9)
- RIIQ Lower Respiratory Symptom scores (cough, short of breath, coughing up phlegm (sputum) and wheezing) and the respective AUC (see Section 5.5.1.) was added
- The AUC for the change from Day 1 for PGI-H and the AUC for PGI-C and PGI-S, will be calculated (see Section 5.5.2)

### 5. REVACCINATION SUBCOHORTS AND SECOND AND THIRD RSV SEASON ANALYSIS

The main focus of the year two and three analysis will be RT-PCR confirmed RSV positive ARIs.

Due to the measures implemented against the COVID-19 pandemic in the regions that the study is conducted, the number of RSV reported cases might be limited during the second and/or third RSV season. In such case, the efficacy analysis of year two and/or three will be restricted to a few key tables or listings. In case no RSV cases are reported, then the end of season two and/or three analysis might be restricted to only safety and immunogenicity. At the 'End of Efficacy Study Analysis' results will still be presented across the three year period, however.

#### 5.1. SUBJECT INFORMATION

Demographic characteristics, disposition information, protocol deviations and concomitant medications will be summarized in a similar way to season one for the Revaccination Subcohorts. Some tables might also be created for the PPE sets for the second and third RSV season..

Comorbidities and medical conditions of interest will also be summarized at Day 365/Day 730.

The time that participants are followed in the study will be summarized descriptively, for the FAS and the PPE across the three RSV seasons. The time that participants are followed in the study based on the FAS is defined as the time between vaccination and the minimum between study completion, discontinuation or database cut off. The time that participants are followed in the study based on the PPE across three RSV seasons is defined as the time between vaccination and the minimum between study completion/discontinuation or database cut off or in case the participant had a major protocol deviation impacting efficacy during the second or third year respectively the end of the first RSV Season visit (or first RSV Season cut-off of 20 March 2020

if there would be no visit available) or the day before the planned Day 730 visit (or relative day 730 if no planned day 730 is present) is used. Additionally for participants in Revaccination Subcohort A or B, the end of the first RSV Season visit (or first RSV Season cut-off of 20 March 2020 if there would be no visit available) or the day before the planned Day 730 visit (or relative day 730 if no planned day 730 is present) is used respectively.

## 5.2. SAFETY

Safety analyses for the second and third RSV season will be performed similarly to the first RSV season (see Section 4.2), based on the FAS. The analysis of solicited and unsolicited AEs will be restricted to the Revaccination Subcohorts.

For the analysis of serious AEs (SAEs) the entire FAS will be used. **For participants who will not receive a revaccination**, all SAEs will be reported from administration of study vaccine on Day 1 until the end of the first RSV season (or 6 months after vaccination, whichever comes later). In addition, SAEs classified as related to the study vaccine, SAEs resulting in death, (S)AEs resulting in study discontinuation, and (S)AEs resulting from procedures and non-investigational (concomitant) Janssen products will be collected during the entire study for all participants. For these participants, SAEs associated with ARIs and complications related to ARIs that classify as SAEs will be collected from the Day 365 (Month 12) visit until the end of the second RSV season, from the end of the second RSV season until the Day 730 (Month 24) visit, and from the Day 730 (Month 24) visit until the end of the third RSV season.

In the Revaccination Subcohorts B, C and D from 1st revaccination onwards and in Revaccination Subcohort 2A from d730 onwards, thrombosis with thrombocytopenia syndrome (TTS) is to be reported to the sponsor as an adverse event of special interest (AESI), within 24 hours of awareness. A potential AESI is defined as thrombotic events or symptomatic thrombocytopenia. For the analysis of serious AEs (SAEs) and (potential) AESIs in the Revaccination Cohorts the FAS will be used as well.

For Revaccination Subcohort A, all SAEs will be reported from administration of study vaccine on Day 1 until the end of the first RSV season (or 6 months after vaccination, whichever comes later), and from the time of revaccination at Month 12 until the end of the second RSV season, or until 6 months after revaccination, whichever comes later. For Revaccination Subcohort 2A, all SAEs and AESIs will also be collected from the time of revaccination on Day 730 until 6 months after revaccination. For the other Revaccination Subcohorts (B, C, and D), SAEs and AESIs will be collected from the time of revaccination until 6 months thereafter. In addition, SAEs classified as related to the study vaccine, SAEs resulting in death, (S)AEs resulting in study discontinuation, and (S)AEs resulting from procedures and non-investigational (concomitant) Janssen products will be collected during the entire study for all participants. For the participants in the Revaccination Subcohorts C and D, these (S)AEs will be collected retrospectively for the time period between the last end of the RSV season visit and the revaccination upon the day of revaccination. For all Revaccination subcohorts, collection of SAEs associated with ARIs and complications related to ARIs that classify as SAEs will stop at the end of the second RSV

season for Subcohort A, on Day 730 (Month 24) for Subcohort B, and at the latest at the end of the third RSV season for Subcohorts C and D.

Different types of SAE tables will be created:

- one focusing on all FAS participants by period until the end of the study or until revaccination.
- one focusing on each Revaccination Subcohort, from revaccination onwards until the end of the study by period.

For related SAEs, SAES resulting in death and AEs leading to discontinuation, tables as described above or listings (depending on the number of occurrences) may be provided.

For AESI analyses, the following subcategories are defined:

- Potential AESIs as identified by the investigator in the database
- Potential AESIs selected programmatically. Those include all reported AEs that are identified by the selection rule:
  - SMQ (Standardised MedDRA Queries) = “EMBOLIC AND THROMBOTIC EVENTS (SMQ)”  
or
  - (SUB\_SMQ1 = “HAEMATOPOIETIC THROMBOCYTOPENIA (SMQ)” and SCOPE in (“BROAD”, “NARROW”)) or HLT (higher level term)=”Thrombocytopenias”
- Potential AESIs qualified for assessment  
Potential AESIs (programmed/identified by the investigator) that have risk levels assessed by one of the following three criteria are considered ‘qualified for assessment’:
  - Brighton Collaboration Level (Level 1-5)
  - CDC Tier (non-tier 1/2, tier 1, tier 2)
  - PRAC criteria (confirmed, possible, probable, unlikely, criteria not met)

As AESI (potential, identified by the investigator and/or qualified for assessment) are only collected in the Revaccination Subcohorts B, C and D from 1st revaccination onwards and in Revaccination Subcohort 2A from Day 730 onwards, the analysis of these potential AESI will only include these cohorts/timepoints. Potential AESIs as identified by the investigator, will be tabulated according to the following categories: ‘Embolic and thrombotic events (SMQ; Standardised MedDRA Queries)’ and ‘Haematopoietic Thrombocytopenia (SMQ) (broad) or HLT (higher level term) = ‘Thrombocytopenias’, and ‘Other’. Potential AESI as identified by the investigator, related to study vaccine (investigator assessment), will be tabulated similarly. Potential AESIs qualified for assessment will be tabulated by categories: ‘Embolic and thrombotic events (SMQ)’ and ‘Haematopoietic Thrombocytopenia (SMQ) (broad) or HLT=Thrombocytopenias’.

In addition to the potential AESIs as identified by the investigator in the database, potential AESIs will also be selected programmatically. Those will be tabulated by categories: ‘Embolic

and thrombotic events (SMQ)' and 'Haematopoietic Thrombocytopenia (SMQ) (broad) or HLT=Thrombocytopenias'. Potential AESI determined programmatically, related to study vaccine (investigator assessment), will be tabulated similarly. For these, all cohorts and the whole study period will be included in the analyses.

All AESI analyses will be presented by phase as well as by time interval. The definition of the different time intervals can be found below.

Dose	Interval	From	to
Post-vaccination 1	0-28 days post-dose	Date time of the 1 st vaccination	Min of: * 
 
• 23:59 at the date of last contact (for discontinuations)
 
• 23:59 at date of DB cut-off for interim analyses
 
• Maximum (Date of Vaccination 1 + 28 days at 23:59 , date of scheduled visit 4 weeks after 1st vaccination at 23:59)
 

	29-56 days post-dose	One minute after the end of the interval 0-28 days post dose	Min of: 
 
• 23:59 at date of last contact (for discontinuations)
 
• 23:59 at date of DB cut-off for interim analyses
 
• Date of Vaccination 1 + 56 days at 23:59
 

	57 days - 6 months post-dose	One minute after the end of the interval 29-56 days post-dose	Min of: 
 
• 23:59 at date of last contact (for discontinuations)
 
• 23:59 at date of DB cut-off for interim analyses
 
• Maximum (Date of Vaccination 1 + 168 days at 23:59 , date of scheduled visit 168 days post 1st vaccination at 23:59 )
 

	>6 months post-dose	One minute after the end of the interval 57 days - 6 months post-dose	Min of: 
 
• 23:59 at the date of last contact (for discontinuations)
 
• 23:59 at the date of DB cut-off for interim analyses
 
• 1 min prior to date time of vaccination 2 for participants in the Revaccination Subcohorts
 

Post-vaccination	0-28 days	Date time of the	Min of: *

2	post-dose	2 nd vaccination	
 
• 23:59 at the date of last contact (for discontinuations)
 
• 23:59 at date of DB cut-off for interim analyses
 
• Maximum (Date of Vaccination 2 + 28 days at 23:59 , date of scheduled visit 4 weeks after 2nd vaccination at 23:59 )
 

	29-56 days post-dose	One minute after the end of the interval 0-28 days post-dose	Min of: 
 
• 23:59 at date of last contact (for discontinuations)
 
• 23:59 at date of DB cut-off for interim analyses
 
• Date of vaccination 2 + 56 days at 23:59
 

	57 days - 6 months post-dose	One minute after the end of the interval 29-56 days post-dose	Min of: 
 
• 23:59 at date of last contact (for discontinuations)
 
• 23:59 at date of DB cut-off for interim analyses
 
• Maximum(Date of vaccination 2 + 168 days at 23:59 , Day 533 visit at 23:59)
 

	>6 months post-dose	One minute after the end of the interval 57 days - 6 months post-dose	Min of: 
 
• 23:59 at the date of last contact (for discontinuations)
 
• 23:59 at the date of DB cut-off for interim analyses
 
• 1 min prior to date time of vaccination 3 at 23:59 for participants in Revaccination Subcohorts 2A and 2B
 

Post-vaccination 3	0-28 days post-dose	Date time of the 3 rd vaccination	Min of:* 
 
• 23:59 at the date of last contact (for discontinuations)
 
• 23:59 at date of DB cut-off for interim analyses
 
• Maximum(Date of vaccination 3 + 28 days at 23:59 , date of scheduled visit 4 weeks after 3rd vaccination at 23:59 )
 

	29-56 days post-dose	One minute after the end of the interval 0-28 days post-dose	Min of: 
 
• 23:59 at date of last contact (for discontinuations)
 
• 23:59 at date of DB cut-off for
 

			interim analyses 
 
• Date of vaccination 3 + 56 days at 23:59
 

	57 days - 6 months post-dose	One minute after the end of the interval 29-56 days post-dose	Min of: 
 
• 23:59 at date of last contact (for discontinuations)
 
• 23:59 at date of DB cut-off for interim analyses
 
• Maximum(Date of vaccination 3 + 168 days at 23:59 , Day 898 visit at 23:59 )
 

	>6 months post-dose	One minute after the end of the interval 57 days - 6 months post-dose	Min of: 
 
• 23:59 at the date of last contact (for discontinuations)
 
• 23:59 at the date of DB cut-off for interim analyses
 

The combination of the '0 - 28 days post-dose' interval and the '29 - 56 days post-dose' interval will be referred as '0 - 56 days post-dose'.

The combination of the '0 - 28 days post-dose' , '29 - 56 days post-dose' and '57 days - 6 months post-dose' intervals will be referred as '0-6 months post-dose'.

\*In case the '0 - 28 days post-dose' interval ends later than 56 days post vaccination then the '29 - 56 days post-dose' interval is not required. For example, if a participant had Day 29 visit at relative day 57, then the following intervals will be created:

0 - 28 days post-dose, lasting from 0 to relative day 57,

57 days - 6 months post-dose, lasting from 58 onwards.

In case the definitions of the time intervals cause overlap, the start date of the latter time interval should always start one minute after the end of the previous one.

For potential AESIs qualified for assessment, potential AESIs as identified by the investigator and potential AESIs determined programmatically, attribution to the intervals will be done similarly to the unsolicited AEs as described in Section 4.2.1.3. For Step 2 of phase allocation of adverse events, the '0 - 28 days post-dose' interval should be treated similar to 'active' periods and the rest as 'non- active' periods.

Further, for solicited AEs, the denominator for the percentages will be the number of participants with data assessed by the PI in the considered population and phase for a certain regimen (incidence per 100 participants/phase) and risk level.

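### The qualified-for-assessment AESI table admits events because a TTS assessment exists, not because of its result, so supported and rejected cases share rows

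*SAP*

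**What the plan says.** All the relevant text is in SAP Section 5.2 (Safety).

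- **The event of interest.** For Revaccination Subcohorts B, C and D from the first revaccination, and 2A from Day 730, "thrombosis with thrombocytopenia syndrome (TTS) is to be reported to the sponsor as an adverse event of special interest (AESI").
- **The wider net.** "A potential AESI is defined as thrombotic events or symptomatic thrombocytopenia". Either component is enough.
- **Three subcategories.** Potential AESIs are identified by the investigator, selected by program from MedDRA groupings, or counted as qualified for assessment. An event from either of the first two sources joins the third group if it is among those "that have risk levels assessed by one of the following three criteria are considered" qualified.
- **The scales.** "Brighton Collaboration Level (Level 1-5"), "CDC Tier (non-tier 1/2, tier 1, tier 2") and "PRAC criteria (confirmed, possible, probable, unlikely, criteria not met").
- **The table.** "Potential AESIs qualified for assessment will be tabulated by categories". The two categories are the embolic and thrombotic SMQ, and the thrombocytopenia SMQ (broad) or HLT.
- **Other breakdowns.** "All AESI analyses will be presented by phase as well as by time interval". Through Section 4.2, safety output is also given by regimen and risk level.

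**The concern.** TTS is the combination of thrombosis and thrombocytopenia. The third subcategory is the only place in the SAP that uses a formal TTS assessment, so a reader would expect its table to report what the assessment found. It does not. The result serves only as an entry ticket and is then left out of the display.

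An assessed thrombotic event that did not meet the criteria counts the same as one that was confirmed. In a trial of people aged 65 or over, a count of assessed thrombotic events is hard to interpret without the result beside it. Section 3.1 tells the IDMC to focus specifically on AESIs in Subcohorts 2A, B, C and D, so this is a safety question the trial has itself singled out.

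**Working it through.** The SAP gives no figure to reproduce. The check compares the entry rule with the tables.

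**1. Which results admit an event?**

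| Scale | Results listed | Number | Negative on their face |
|---|---|---|---|
| Brighton | Levels 1 to 5 | 5 | SAP does not say |
| CDC | non-tier 1/2, tier 1, tier 2 | 3 | non-tier 1/2 |
| PRAC | confirmed, possible, probable, unlikely, criteria not met | 5 | unlikely, criteria not met |

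Total: 5 + 3 + 5 = 13 results. The rule asks only that a level was assessed, so all 13 admit an event. At least three of them point away from TTS by their own label.

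**2. Which tables use the result?** Section 5.2 specifies five AESI tables.

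| Table | Rows |
|---|---|
| Investigator-identified | thrombotic; thrombocytopenia; other |
| Investigator-identified, related to vaccine | same |
| Qualified for assessment | thrombotic; thrombocytopenia |
| Selected by program | thrombotic; thrombocytopenia |
| Selected by program, related to vaccine | same |

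None of the five is split by Brighton level, CDC tier or PRAC class. The three scales are mentioned nowhere else in the SAP.

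**3. What can the rows distinguish?**

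- *Result.* Take two thrombotic events, one classed PRAC confirmed and one classed criteria not met. Both are qualified and both fall in the thrombotic row.
- *Combination.* Suppose the two components are coded as two events. One participant with both adds 1 to each row. Two participants with one component each also add 1 to each row. The rows are identical.
- *Linking of events.* Step 2 of Section 4.2.1.3, which Section 5.2 applies to AESIs, joins only events with the same preferred term. It does not join a thrombosis to a thrombocytopenia.

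A total row counting participants with any category would allow the overlap to be worked out, but Section 5.2 does not specify one. Even then the overlap would not carry the assessment result.

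**4. Who is affected?** From Table 1, the planned participants under AESI collection are 120 (2A) + 270 (1B and 2B) + 240 (1C and 2C) + 240 (1D and 2D) = 870. Without C and D, whose continuation is conditional, the number is 120 + 270 = 390.

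**The case against.** The strongest reply is that these tables are not the only route to a TTS case. TTS must be reported to the sponsor within 24 hours of awareness (Section 5.2), and IDMC members are informed of AESIs (Section 3.1). SAEs are tabulated by preferred term, with listings or narratives as appropriate for deaths and for severe or serious events (Section 4.2.1.2). SAE tables are also planned for each revaccination subcohort from revaccination onwards (Section 5.2). Table layouts are left to separate data presentation specifications (Section 1), which could add a breakdown.

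This stands, and it limits the point. A reader might infer that the planned output cannot show whether any TTS occurred. The documents do not support that: a case could surface by any of these routes. The two-row split also carries some information, because an empty thrombocytopenia row would be evidence against reported TTS in that set. The ambiguity arises mainly when both rows are filled.

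The category name is also not false. It speaks of potential events and never claims confirmed TTS, and safety is descriptive with no formal comparison.

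The reply does not remove the gap. Nothing in the SAP connects the SAE tables, listings or narratives to the Brighton, CDC or PRAC result. Section 1 says the SAP holds all the information needed for a full safety analysis, and Section 5.2 already fixes the rows of this table without the result.

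**Conclusion.** The point holds for the AESI tables of Section 5.2. All 13 possible results admit an event, and none of the five tables reports by any of them. Those tables therefore do not separate events whose assessment supports TTS from events whose assessment rejects it, and they do not identify participants with both components. This is a stated tabulation rule that discards the result needed to read the table, not merely missing detail. It is a worthwhile correction, not a threat to participant safety or to the trial's conclusions on efficacy.

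The conclusion rests on the text alone. The combination argument assumes that the two components are coded as separate events. I give no expected number of events or probability of a misleading table. The SAP states neither a background rate nor the share of potential AESIs that will be assessed, and the relevant quantity would be events in both rows, not in either. The SAP also does not say which Brighton levels count as a TTS case, so I make no claim on that.

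**What to change.** In Section 5.2 and the matching data presentation specification:

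1. Tabulate qualified events by assessment result (each Brighton level, CDC tier and PRAC class) per regimen, phase and time interval. If there are few events, a listing with the same fields will do.
2. Show PRAC criteria not met, PRAC unlikely and CDC non-tier 1/2 separately from the other results.
3. Add a participant-level row for those whose assessment supports TTS. The sponsor should prespecify the qualifying levels on each scale before the database lock of the relevant analysis. Database lock is the practical reference point because the revaccination and end-of-efficacy analyses use unblinded data (Sections 3.3 and 3.5 to 3.7).
4. Keep the thrombotic and thrombocytopenia split as a secondary breakdown.

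The cost is a wording change and one extra table or listing. No new assessment should be needed, since the qualified group cannot be formed without knowing which events have a result. That is an inference: the SAP does not say where the results are held, and the sponsor should confirm it.
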